**Impact of Individualized Estrogen Therapy on Cardiovascular Disease Risk Parameters in
Young Women after Bilateral Oophorectomy: A Randomized Controlled Trial**

NCT03815929

January 29, 2021

Specific aims: Women undergoing bilateral oophorectomy before the natural age of menopause (~51 years) have a higher risk of early mortality in comparison to their age-matched counterparts with intact ovarian function.[1-4] The increase in mortality is primarily related to an increased risk of cardiovascular disease (CVD).[5] The risk can be mitigated, in part, with the use of estrogen-based hormone therapy (ET) given at least until the natural age of menopause, unless there is a contraindication to its use.[1, 5-7] While most professional societies support the use of ET in this group of women, there are no consensus guidelines regarding the optimal estrogen dose required to minimize risk for early mortality, multiple morbidities and accelerated aging, or recommendations regarding how to individualize treatment (tailored to estradiol level) in these young women.[6] The **long-term goal** of this work is to improve and individualize the hormonal treatment of women with bilateral oophorectomy, in order to reduce mortality, CVD risk and other morbidities associated with premature estrogen deprivation. To achieve this goal, we will test the *over-arching hypothesis that an individualized approach to dosing estrogen treatment in young women (<46 years of age) after bilateral oophorectomy would improve parameters of CVD risk*. Current clinical practice is to treat with a dose of estrogen about 2-4 fold higher than that used for vasomotor symptoms in women after natural menopause. While the dose is often increased based on symptoms, this approach is not systematic and the time required to establishing an appropriate dose may be unacceptably prolonged. Furthermore, although symptoms are ameliorated by this approach, it is unclear whether an appropriate dose is reached to mitigate CVD risk and mortality. Therefore, we are proposing to study the impact of hormone therapy on measures of cardiovascular function in young women after bilateral oophorectomy. We will recruit women younger than 46 years of age who undergo bilateral oophorectomy, and are candidates for hormone therapy after the procedure. We will study whether titrating the dose of estradiol to achieve the average premenopausal estradiol level (80-120 pg/ml) is superior to “standard dosing” for improving CVD risk parameters. We will focus on measures of cardiovascular function which show rapid changes to hormonal variation, and are predictors of CVD progression: arterial stiffness, and cardiovascular response to sympathetic stressors. Our over-arching hypothesis will be tested by the following specific aims:

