5. For Time Controls: Are currently pregnant or lactating, or are of child-bearing potential or are likely to become pregnant during the study and unwilling to use contraception; Acceptable forms include:
 - a. Barrier methods (such as a condom or diaphragm) used with a spermicide (a foam, cream, or gel that kills sperm)
 - b. Copper IUD
 - c. Hysterectomy
 - d. Tubal ligation
 - e. Abstinence (no sex)
6. Any condition or factor judged by the investigator to preclude participation in the study

Study Design and Procedures: This will be a randomized open-label trial. Participants will be randomized 1:1 to one of 2 groups, distinguished by the **estradiol replacement therapy regimen**. One group will receive the standard 100 mcg or lower transdermal estradiol patch as clinically indicated (or an equivalent oral dose; n=up to 25). The other group will be on transdermal (or oral) estradiol therapy titrated to achieve a serum estradiol level of 80-120 pg/ml (n=up to 25). Participants with an intact uterus will also be prescribed a progestogen for endometrial protection. A third group of healthy age-matched premenopausal women, not on any hormonal contraception will be recruited via an advertisement, and will be studied as time controls (n=up to 10).

The women deemed eligible based on the phone screen will be scheduled for a baseline medical assessment by an MD in the Mayo Clinic Menopause and Women's Sexual Health Clinic (MWSH). This is a normal part of clinical care for these women prior to oophorectomy. This visit will occur after they have been evaluated in the Department of Gynecology, and a decision to proceed with bilateral (or completion) oophorectomy has been made. Relevant past history including history of pregnancy induced hypertension and gestational diabetes will be obtained. If the patient is eligible and interested in study participation, they will meet with a study team member who will review the informed consent and answer all of the patients' questions.

After they agree to participate and sign the consent form, they will complete questionnaires to assess the following (these questionnaires will also be assessed at 6 and 12 month visits):

- a. *Menopausal symptoms severity: Menopause Rating Scale (MRS)*. This self-reported questionnaire consists of 11 items covering psychological, somatic, and urogenital subscales. It can be easily administered and scored, and completed in less than 5 minutes.

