We will ask participants to collect 24h urine sample. A mail-in kit will be sent to the participant, and clear instructions for collection will be provided. Participants on any kind of exogenous glucocorticoid therapy will be excluded from this part of the study. Urine samples will be aliquoted and stored as a part of the IRB # 13-005838 biobank. Urine steroid profiling will be performed in batches in the ICL lab.

The participants will then be asked to report to the clinical research and trials unit (CRTU) for the baseline study visit. When they report to the CRTU for the baseline visit, they will be in the fasting state (8 hours) to complete the tests listed below. Participants will also refrain from vigorous exercise, caffeine, and alcohol for 24 hours prior to the study days.

[figure not shown]
Baseline Study Day Protocol:

1. ***Urine Pregnancy Test:*** Urine Pregnancy tests will be performed on subjects determined to be of child-bearing potential. Nurses in the CRTU will assess the need for this, and confirm through a pregnancy test their status before beginning physiological testing.
2. ***Blood sampling:*** Baseline blood samples will be collected for estradiol, estrone, testosterone (total and free), glucose, insulin, lipid panel, norepinephrine, a bone alkaline phosphatase and HbA1c. We will also plan to store 5 ml each of serum and plasma for future testing, including genomic studies.. The norepinephrine test will be omitted for the limited participation subjects.
3. ***Dual energy x-ray absorptiometry (DXA):*** Body composition will be measured prior to the study visit in the CTSA body composition core using DXA. All subjects will have whole-body and regional fat and fat-free mass measured by regional analysis of whole-body DXA scans with Lunar software. (Baseline DXA scan for the limited participation subjects can be done within a month after oophorectomy.)

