Surgery and dismissal: Participants will be randomized 1:1 to one of the 2 groups upon dismissal from the hospital after bilateral oophorectomy: standard dose estradiol, (including dosing dictated by personal medical history) or titrated dose estradiol therapy. Women with an intact uterus will also be prescribed a progestogen for endometrial protection. The preferred progestogen will be oral micronized progesterone, given as oral dose 100 mg daily or 200 mg cyclically during the first 12 days of month. Women belonging to the titrated dose ET group will initially be dismissed on the standard 100 mcg transdermal estradiol patch. They will have their estradiol levels checked once every 3-4 weeks (clinical visits overseen by our MD investigators in the Menopause and Women's Sexual Health Clinic) and the estradiol dose accordingly titrated until they reach the desired goal of an estradiol level of 80-120 pg/ml. If women in the standard dose group report residual symptoms despite treatment, we will offer titration to a higher dose of ET. Women intolerant of the estradiol patch will be treated with oral estradiol at an equivalent dose. Women with intolerance/side-effects/abnormal uterine bleeding with progesterone will be offered an alternative progestogen for uterine protection. Clinical care of the subjects will be overseen by clinical care providers in the Menopause and Women's Sexual Health Clinic.

The study is designed to have active study participants on varying hormone replacement after oophorectomy as dictated by their clinical needs.

Post-operative Study Visit at 6 Months: The same protocol will be followed as the baseline study day protocol above except we will not check glucose, lipids and insulin levels, and DXA scan will not be performed, as it will take longer than 6 months to see changes in these measures. Blood samples drawn for levels of estradiol and estrone will ideally be drawn on the second day after application of a new patch.

Post-operative Study Visit at 12 Months: Subjects will report to the clinical research and trials unit (CRTU), and the same protocol will be followed as that of the baseline study day visit. All blood samples will be drawn in

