the same way as done for the baseline visit. A 24-hour urine sample will be collected again in a mail-in kit as described above. Participants on any kind of exogenous glucocorticoid therapy will be excluded from this part of the study. Urine samples will be aliquoted and stored as a part of the IRB # 13-005838 biobank. Urine steroid profiling will be performed in batches in the ICL lab.

Time controls will complete baseline, 6 month, and 12 month study visits.

Participant Retention: All participants will be remunerated up to \$300. Participants will be remunerated \$100 for each of the following visits: baseline, six months and twelve months. If a participant refuse the cardiovascular testing, and chooses the option to complete the blood-work, questionnaires and DXA scan only, they will be remunerated \$50 for each of the following visits: baseline, six months and twelve months. Amounts will be prorated according to the visits the participant completes. In addition, participants will be provided with Mayo parking vouchers for the time they are onsite for study visits. For CRTU visits, participants will be given six-hour vouchers, and for other visits participants would be given 2 hour parking vouchers. After the long visits in the CRTU, which requires fasting for 8 hours, participants will be provided a meal.

Statistics (prepared in collaboration with [name], Ph.D.): For the proposed investigation, women 21-45 years of age undergoing bilateral oophorectomy will be randomized to one of two groups, based on the regimen of estradiol replacement therapy (standard versus titrated). In addition to estradiol, patients who do not undergo hysterectomy will receive a progestogen as clinically indicated. A randomization schedule will be generated by the Section of Biostatistics using varied blocked randomization to attain an equal number of women assigned to each treatment group. Covariates not balanced through randomization, such as additional hormone use in patients with hysterectomy, will be accounted for in analysis. For all aims, the primary analyses will be performed using intention to treat with **estradiol dosing regimen** as the *treatment group variable* and secondary analyses will be performed using the **serum estradiol concentration (E2)** as a *continuous explanatory variable*.

Statistical Analysis:

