Summary and Significance: This novel clinical study proposes an individualized approach to hormonal management of women with premature estrogen deprivation. We hypothesize that an individualized approach, tailored to a target estradiol level is more likely to effectively mitigate CVD risk in the young women under study. The results from the current study have the potential to significantly impact the current clinical practice related to the care of young women undergoing bilateral oophorectomy. Furthermore, there is potential for extrapolating these principles to the care of women experiencing premature menopause due to non-surgical causes (primary ovarian insufficiency).

Limitations: Women with an intact uterus after oophorectomy will be on a progestogen in addition to ET for endometrial protection. It is conceivable that the progestogen may impact some of the parameters under study. We are hypothesizing that each woman will serve as her own control and the baseline measurements will be compared to the measurements obtained on estrogen therapy.

Future plans: The current study will provide pilot data regarding the impact of individualized estradiol therapy on CVD risk parameters in young women after bilateral oophorectomy. Our next step would be to obtain extramural funding in order to pursue a larger-scale study to evaluate the effect of individualized estradiol therapy on other long-term health consequences in young women with bilateral oophorectomy, including blood pressure control, changes in metabolic profile (including glycemic control and lipid profile), cognitive function, mood, quality of life and sexual function. We also intend to expand our study population to include women with premature estrogen deprivation due to non-surgical causes, i.e., those with primary ovarian insufficiency, or ovarian failure due to chemotherapy or radiation. It is conceivable individualized hormone therapy, targeted to estradiol levels, will become the standard of care in women with premature estrogen deprivation.

REFERENCES

1. Faubion, S.S., et al., *Long-term health consequences of premature or early menopause and considerations for management*. Climacteric, 2015. **18**(4): p. 483-91.
2. Rocca, W.A., et al., *Survival patterns after oophorectomy in premenopausal women: a population-based cohort study*. Lancet Oncol, 2006. **7**(10): p. 821-8.

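### Cheap precision gain: menstrual-cycle phase is neither scheduled nor recorded at premenopausal visits, which mainly blurs the time controls' change over 12 months

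*Combined protocol and SAP*

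**What the plan says.** The Specific aims give the reason for the choice of outcomes: "We will focus on measures of cardiovascular function which show rapid changes to hormonal variation". All women are premenopausal at baseline. The third group, of up to 10, consists of "healthy age-matched premenopausal women, not on any hormonal contraception" (Study Design and Procedures), and the 12-month visit section adds: "Time controls will complete baseline, 6 month, and 12 month study visits".

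Before each study day, participants fast for 8 hours and avoid vigorous exercise, caffeine and alcohol for 24 hours. Tonometry follows about 15 minutes of supine rest. On hormones, the Baseline Study Day Protocol says "Baseline blood samples will be collected for estradiol, estrone, testosterone (total and free), glucose, insulin, lipid panel" and goes on to other analytes. Progesterone and LH are not listed.

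The plan does attend to hormonal timing on treatment. For the 6-month visit it says: "Blood samples drawn for levels of estradiol and estrone will ideally be drawn on the second day after application of a new patch". There is no counterpart for visits at which the ovaries are still the source of estradiol. No text sets a cycle window, asks for the last menstrual period or cycle day, or names phase as a covariate.

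Under Limitations, the plan relies on baseline: "each woman will serve as her own control", with baseline values compared with those on estrogen therapy.

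**The concern.** If the outcomes move quickly with hormones, a premenopausal woman's reading depends partly on where she is in her cycle. A visit at an arbitrary phase adds variance unrelated to time or treatment.

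The time controls are most exposed. Their name implies that they show how the measures drift over 12 months without surgery. Each estimate of drift is a difference between two visits, and both visits carry phase noise. No surgery date constrains when they are seen, so this variance is largely avoidable.

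For surgical participants only the baseline visit is affected, because no ovarian cycle remains at 6 and 12 months. Noise there weakens baseline as a covariate and adds to each woman's change from it. The study is also meant as pilot data for a larger trial, so an inflated SD of change could carry into that trial's design.

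**Working it through.** **The plan's own figure.** The sample-size section gives 25 per group, a difference of 0.75 SD, one-tailed alpha 0.05 and power 82%. A two-sample t-test (noncentral t, 48 degrees of freedom, noncentrality 0.75 × √(25/2) = 2.65) gives 83.4%, which reproduces it closely. No baseline value enters this calculation.

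**Assumed inputs.** The documents give neither a phase variance nor a baseline-to-follow-up correlation. Take outcome variance 1 with phase fixed, correlation r between baseline and 12 months with phase fixed, and phase adding a fraction f to the variance at a premenopausal visit, independently between visits. The main case is r = 0.7, f = 0.25; f is varied from 0.10 to 0.50.

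**Time controls (n = 10, phase noise at both visits).** SD of change = √(2(1+f) − 2r). The 95% half-width for mean change = 2.262 × SD/√10, where 2.262 is the t quantile on 9 degrees of freedom.

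| f (r = 0.7) | SD of change | Ratio to f = 0 | Half-width (SD units) |
|---|---|---|---|
| 0 | √0.6 = 0.775 | 1 | 0.55 |
| 0.10 | √0.8 = 0.894 | 1.15 | 0.64 |
| 0.25 | √1.1 = 1.049 | 1.35 | 0.75 |
| 0.50 | √1.6 = 1.265 | 1.63 | 0.90 |

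At f = 0.25 the half-width equals the 0.75 SD difference that the trial is sized to detect between arms. With other correlations and f = 0.25, it goes from 0.715 to 0.876 (r = 0.5) or from 0.452 to 0.679 (r = 0.8).

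**Randomised arms (phase noise at baseline only).**

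- Unadjusted 12-month comparison: baseline is not used, so power stays at 83.4% for any f.
- Baseline-adjusted model: the correlation falls to r/√(1+f), and the residual SD is √(1 − r²/(1+f)).
- Change score: SD = √(2 + f − 2r).

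Power in each case uses the same t-test, with 0.75 divided by the relevant SD:

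| f (r = 0.7) | Adjusted: residual SD | Adjusted: power | Change score: SD | Change score: power |
|---|---|---|---|---|
| 0 | 0.714 | 97.8% | 0.775 | 95.8% |
| 0.10 | 0.745 | 96.9% | 0.837 | 93.0% |
| 0.25 | 0.780 | 95.6% | 0.922 | 88.3% |
| 0.50 | 0.821 | 93.8% | 1.049 | 80.2% |

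The adjusted model loses 0.9 to 4.0 points and stays above the planned 82% throughout. A change-score comparison loses 2.8 to 15.6 points. The same SDs describe within-woman change from baseline, which widens by 8% to 35% (0.837/0.775 to 1.049/0.775).

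**The case against.** The strongest reply is that the primary result is untouched. Randomisation takes place at hospital dismissal, after baseline, so phase at baseline is balanced in expectation. By 12 months neither randomised group has an ovarian cycle. The stated power does not depend on baseline. All of this stands.

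A reader might still infer that the trial loses part of its sample. At r = 0.7 and f = 0.25, the relative efficiency of the adjusted analysis is (1 − 0.49)/(1 − 0.49/1.25) = 0.839, which turns 50 women into about 42. That is a loss against an ideal adjusted analysis that the plan neither specifies nor relies on. The same inputs move adjusted power only from 97.8% to 95.6%.

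Two extensions are also tempting and weak:

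- *Baseline estradiol is a noisy predictor.* Aim 2 concerns women already on replacement, and the Statistics section does not say that the endogenous baseline level is the predictor. If it were, estradiol and outcome would be measured at the same visit, so cyclic variation would be partly signal.
- *Visits should be timed to the cyclic progestogen, given as* "200 mg cyclically during the first 12 days of month". If this means the calendar month, visit date and prescribed regimen already show it. It concerns only women with a uterus who take the cyclic option.

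For the controls, the reply is that random phase has no systematic direction and that the plan names no analysis using them. The first part is right: the harm is a wider interval, not false drift in one direction. The second does not help, since a group recruited for three visits is presumably meant to yield an estimate.

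Estradiol is measured at each visit, and serum and plasma are stored, so hormonal state is partly captured. A single estradiol value without cycle day or progesterone does not identify phase. Finally, the absence of recording is inferred from the text: history-taking at baseline is open-ended, and the two figures are not available.

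**Conclusion.** The point holds as a cheap improvement in precision. The plan standardises several lesser influences on outcomes picked for hormonal responsiveness, yet leaves the cycle unscheduled and unrecorded.

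The material cost is in the time controls, where the interval for mean change could be about 15% to 63% wider at r = 0.7 for f between 0.10 and 0.50. In the randomised arms the cost is nil for an unadjusted 12-month comparison and small with baseline adjustment. It is larger only for change from baseline. Every size rests on assumed values of r and f and on independent phases between visits. If these outcomes vary little over the cycle, the loss is correspondingly small.

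The documents do not support reading this as bias in the arm contrast or as a failure of the stated power.

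**What to change.** 1. In the section on the 12-month visit, where the control visits are listed, state that all three visits of each time control are booked in the same named cycle window.
2. In the Baseline Study Day Protocol, record last menstrual period and cycle day at every premenopausal visit, including all control visits. Add a not-applicable code for women without a usable cycle day. Hysterectomy is accepted among controls, and hormonal contraception is barred only for controls, so some women will need it.
3. In the Statistical Analysis section, pre-specify a sensitivity analysis of change from baseline that takes cycle phase into account.

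The window applies to controls only; for surgical participants, phase is recorded and nothing is rescheduled. The cost is one extra question per premenopausal visit, less flexible booking for at most 10 women, and one sensitivity analysis. The recording should start with the next visit, because cycle day is hard to recover afterwards.

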4. ***Cardiovascular monitoring:*** Electrocardiogram (ECG) and continuous blood pressure will be monitored and recorded throughout the protocol. We will use a Nexfin to record continuous blood pressure. The pneumatic cuff will be placed around the middle finger of the non-dominant hand for continuous, non-invasive monitoring of blood pressure. The Nexfin has previously been reported to accurately record changes in mean arterial pressure (MAP) during both exercise and apnea, and has been used extensively in [name] experiments. The Nexfin cuff will be positioned at heart level and kept at the same level throughout the duration of the study visit. Cardiovascular activity will be recorded using a 3-lead electrocardiogram (Cardiocap) placed in the Lead II configuration.
5. ***Arterial Tonometry:*** Arterial tonometry estimates central blood pressure which is an important determinant of flow through the carotid and cerebral vessels. Additionally, indices of arterial stiffness can be calculated from non-invasive applanation tonometry. Participants will be studied in the supine position after approximately 15 minutes of relaxation. Tonometry transit distances from the supra-sternal notch to the femoral, carotid, and radial recording sites will be measured with a tape measure. High-fidelity pressure waveforms will be recorded non-invasively using a pencil-type Millar Micro-tip pressure transducer from the radial, femoral and carotid arteries in that order in rapid succession. An aortic pressure waveform is derived from the radial pulse using the application of a generalized transfer function (SphygmoCor). Arterial applanation tonometry will then be performed on the radial, femoral, and carotid arteries in rapid succession over a 15 min period. Optimal recording of the pressure wave will be obtained when the hold-down force of the transducer on the artery is such that the resulting waveform has a stable baseline for at least 10 beats.
6. ***Isometric Handgrip Exercise and Post-Exercise Ischemia:*** Maximal Voluntary Contraction (MVC, kg) of the non-dominant arm will be determined as the average of the two highest measurements from 5 trials using a hand dynamometer. Static exercise will consist of squeezing a transducer forcefully enough to consistently maintain a moderate workload (30% MVC; a combination of central command, mechanoreflex, and metaboreflex stimulation) [17, 18]. Visual feedback of force production is provided to the subject. Following

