2 minutes of quiet rest, subjects will complete 2 minutes of static handgrip exercise at 30% MVC, followed by 2 minutes of post exercise ischemia (PEI). PEI will begin at the 2-minute mark of exercise prior to the end of contraction and consists of rapid inflation of an occlusion cuff on the exercising arm proximal to the antecubital fossa to suprasystolic pressure (~220 mmHg); the cuff will remain inflated for 2 minutes. PEI traps local metabolites and preserves activation of metabosensitive afferent nerve endings, thus isolating the metaboreflex from central command and the mechanoreflex [19,20,21,22,23]. Participants will be asked to rate their perceived exertion (RPE) at the end of the exercise (Borg scale; range 6 to 20).

7. **Cold Pressor Test:** The subject's hand will be immersed up to the wrist in ice water (0-4 degrees C) for 3 minutes while changes in blood pressure and heart rate are monitored. The Cold Pressor Test will be used to measure non-specific sympathetic reactivity. In addition, expected large fluctuations in blood pressure will be used to obtain an index of baroreflex sensitivity. If a participant has a history of, or suspected to have Raynaud's phenomenon this test will not be completed.

Figure 2. Approximate Timeline for Study Day Visits

In addition to the groups above, in order to keep an optimum recruitment, we will recruit the women who refuse the cardiovascular testing, for blood-work, questionnaires and DXA scan only.

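### Items 4 and 6 of the study-day protocol, on their natural reading, put the finger blood-pressure cuff downstream of the ~220 mmHg occlusion cuff, so blood pressure could not be recorded during post-exercise ischemia

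*Combined protocol and SAP*

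**What the plan says.** Two items of the Baseline Study Day Protocol bear on this point.

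- **Item 4, Cardiovascular monitoring.** "Electrocardiogram (ECG) and continuous blood pressure will be monitored and recorded throughout the protocol". The Nexfin is the only device named for continuous blood pressure, and its placement is given: "The pneumatic cuff will be placed around the middle finger of the non-dominant hand for continuous, non-invasive monitoring of blood pressure". The cuff is to stay at heart level for the whole visit. Nothing tells staff to change hands.
- **Item 6, Isometric Handgrip Exercise and Post-Exercise Ischemia.** The reference load is defined first: "Maximal Voluntary Contraction (MVC, kg) of the non-dominant arm will be determined as the average of the two highest measurements", out of five trials. The static grip lasts 2 minutes at 30% of that maximum. The ischemia phase follows, by "rapid inflation of an occlusion cuff on the exercising arm proximal to the antecubital fossa to suprasystolic pressure (~220 mmHg"), held for 2 minutes. Its stated purpose is to keep the metabolically sensitive nerve endings active after the grip ends, "thus isolating the metaboreflex from central command and the mechanoreflex".

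The sections on the 6-month and 12-month visits repeat these baseline procedures, with exceptions at 6 months (some blood tests and the DXA scan) that do not touch items 4 and 6.

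**The concern.** A finger cuff needs arterial pulsation in the finger. If it is on the limb that is occluded upstream above systolic pressure, it has nothing to measure until the occlusion is released. The ischemia phase exists to show the blood-pressure response to the metaboreflex alone, and that response would be missing.

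The Specific aims name two cardiovascular domains: arterial stiffness and the response to sympathetic stressors. Handgrip with ischemia is one of only two stressor tests in the second domain. The other is the cold pressor test, and for women with known or suspected Raynaud's "phenomenon this test will not be completed". For them, handgrip with ischemia is the only stressor test. A recording missed at a visit cannot be recovered later, and the Limitations section relies on comparing each woman with her own baseline.

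**Working it through.** The plan states no figure on this point, so the main check is a comparison of the two items.

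**Which arm is which**

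| Element | Side given in the text | Source |
|---|---|---|
| Finger blood-pressure cuff | Non-dominant hand | Item 4 |
| Maximal grip measurement | Non-dominant arm | Item 6 |
| Static grip at 30% of maximum | Not restated | Item 6 |
| Occlusion cuff, ~220 mmHg | The exercising arm, side not restated | Item 6 |
| Change of hand, or a second continuous device | None found | Items 4 to 7 |

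1. The workload is a percentage of a maximum measured in the non-dominant arm. A 30% load is meaningful for the arm in which the maximum was measured. Exercising the dominant arm would mean calibrating it from the other arm's strength, which nothing in the text suggests. The exercising arm is therefore most naturally the non-dominant one. This is an inference, and it is the only one needed.
2. The occlusion cuff is on the exercising arm above the elbow, so the finger cuff is downstream of it.
3. The protocol itself calls the occlusion pressure suprasystolic. No arterial pulse then reaches the finger, and none of the 2 ischemia minutes gives a valid finger pressure.
4. During the 2 grip minutes the sensor is on the squeezing hand. Disturbance is likely, but the documents give no figure for it.

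**Share of the stressor recording, per full visit**

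Total = handgrip 2 + ischemia 2 + cold pressor 3 = 7 minutes.

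- Ischemia, no finger pressure: 2/7 = 28.6%
- Handgrip, at risk of disturbance: 2/7 = 28.6%
- Cold pressor, not shown to be affected: 3/7 = 42.9%

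**Number of tests exposed**

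Group sizes are upper limits (for example "titrated to achieve a serum estradiol level of 80-120 pg/ml (n=up to 25"), so these counts are ceilings.

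- Randomised women, three visits: (25 + 25) × 3 = 150. This matches the total of 150 studies in the Investigative Sequence and Timeline table.
- With time controls: (25 + 25 + 10) × 3 = 180
- Randomised women at 12 months, the primary time point: 25 + 25 = 50

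Not every woman will be tested, because "we will recruit the women who refuse the cardiovascular testing, for blood-work, questionnaires and DXA scan only". The documents give no rate for refusal or dropout. Assuming 10% to 30% of randomised women are not tested:

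- All visits: 150 × 0.9 = 135 down to 150 × 0.7 = 105
- At 12 months: 50 × 0.9 = 45 down to 50 × 0.7 = 35

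**The case against.** The strongest reply is that the conflict is inferred and probably corrects itself. The non-dominant arm is named only for the maximal grip, and the sentence about keeping the cuff at one level concerns height, not which hand. A waveform that vanishes when the occlusion cuff inflates would be obvious at the first test, and a team used to the device would change sides. The true loss could then be a few early tests or none. Figures 1 and 2 could not be read in the text available for this review, and either might show arm placement. The minute shares and test counts describe exposure, not harm. The effect is also narrow: one phase of one stressor test, the same in both groups, with ECG and heart rate still recorded.

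Much of this stands. The same-arm reading is an inference, the documents do not show site practice, and the counts are ceilings that assume the error goes unnoticed. Three things limit it:

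- The inference is the likeliest reading, since the load is defined by the non-dominant arm's maximum.
- Figure 1 is captioned as the study protocol and Figure 2 as an approximate visit timeline. A placement shown in either would still contradict the text of item 4 or item 6.
- Item 4 reports that the device tracks mean pressure accurately during exercise and apnea. Neither condition is occlusion of the monitored limb.

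If staff correct the side informally, the written protocol is still wrong. Operators or visits may then differ in the side they use, which weakens comparison with baseline.

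**Conclusion.** The concern holds. On their natural reading, items 4 and 6 cannot both be followed and still yield blood pressure during post-exercise ischemia. As written, 2 of 7 stressor minutes per full visit (29%) have no finger pressure, and another 2 of 7 are at risk. The ceiling is 150 tests in randomised women, 50 of them at 12 months; with an assumed 10% to 30% untested, this becomes about 105 to 135 and 35 to 45. Fewer would be affected if staff notice the lost signal and move the cuff.

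The conclusion rests on the exercising arm being the arm in which maximal grip was measured, and on no unseen instruction moving the finger cuff. The loss does not bias the randomised comparison. ECG, arterial tonometry and the cold pressor test are not shown to be affected. If the site already uses opposite sides, only the wording is at fault. It should be fixed because the remedy is almost free and the data cannot be recovered afterwards.

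**What to change.** Reconcile items 4 and 6 so that the finger cuff is on the hand opposite the arm used for maximal grip, static grip and occlusion. Either assignment works: finger cuff on the dominant hand with exercise and occlusion on the non-dominant arm, or the reverse. State the arm explicitly for the static grip and for the occlusion, and require the same sides at baseline, 6 months and 12 months.

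The cost is one sentence in item 4, one in item 6, and a line on the visit worksheet to record the sides used. No extra equipment, visit time or participants are needed. For women already tested, the sponsor should establish from the recordings which side was used and whether finger pressure was present during ischemia.
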